2.10 PD and PK/PD analyses

Not applicable.

2.12 Biomarkers

Not applicable.

2.13 Other Exploratory analyses

2.14 Interim analysis

A primary endpoint analysis of the data collected up until Week 16, including the co-primary endpoint (at Week 12) will be performed after the last subject completes their Week 16 visit. Efficacy and safety data up to Week 16 visit for all subjects will be summarized. AE listing will be presented on the entire treatment period i.e. reports AE data collected until last subject week 16 cut-off date.

To address comments from the health authorities an additional full analysis will be performed when all subjects have completed the Week 24 visit.

A full analysis will be performed when all subjects have completed the Week 52 visit, (or premature treatment discontinuation visit). Thereafter, efficacy and safety data collected after Week 52 until the end of study may be reported yearly in separate reports.

Additional analyses may be performed to support health authority interactions, as necessary.

Trial modifications are not planned based on any interim analyses. No aggregated statistical analysis will be performed by actual treatment group prior to W16 PEA.

3 Sample size calculation

The sample size for this study is calculated to ensure an adequate number of subjects for PK analyses and powered efficacy analyses. Approximately 80 pediatric subjects from 6 to less than 18 years of age at randomization will be recruited. Since a 15% screening failure rate is expected, approximately 95 patients will be screened. The study will aim to recruit at least 60 subjects with moderate severity and approximately 20 subjects with severe severity.

Power calculations were performed to support the co-primary endpoints PASI 75 and IGA 0 or 1 response at week 12, and secondary endpoint PASI 90 at week 12, versus placebo (historical control) for the low and high secukinumab dose regimens. The low dose arm with smaller treatment effect is being considered in the power/sample size calculation.

Data from four adult placebo-controlled trials (CAIN457A2302, CAIN457A2303, CAIN457A2308 and CAIN457A2309) and pediatric placebo controlled trials ([Paller et al 2008](#), [Landells et al 2015](#)) were used to estimate the historical placebo response rate. For study CAIN457A2310, a 10% response rate was assumed for PASI 75, IGA 0 or 1 and 8% for PASI 90 response for the placebo group. The 95% upper quantile of predicted number of responders are 7, 7 and 6 subjects, respectively. The assumed placebo response rates were derived accordingly with 40 pediatrics for study CAIN457A2310. Refer to table 3.1 below.

Table 3-1 Placebo response rates from historical secukinumab placebo controlled trials

Adult Placebo controlled trial	Endpoint	Number of subjects with response/ Number of subjects evaluable	Placebo response rate (%)
CAIN457A2302	IGA 0 or 1	6/246	2.4
	PASI 75	11/246	4.5
	PASI 90	3/246	1.2
CAIN457A2303	IGA 0 or 1	9/324	2.8
	PASI 75	16/324	4.9
	PASI 90	5/324	1.5
CAIN457A2308	IGA 0 or 1	0/59	0
	PASI 75	0/59	0
	PASI 90	0/59	0

CAIN457A2309	IGA 0 or 1 PASI 75 PASI 90	0/61 2/61 0/61	0 3.3 0
Pediatric Placebo controlled trial	Endpoint	Number of subjects with response/ Number of subjects evaluable	Placebo response rate (%)
Ustekinumab	PGA 0 or 1	2/37	5.4
Dermatol 2015 (Age 12 to 17 years)	PASI 75 PASI 90	4/37 2/37	10.8 5.4
Etanercept NEJM 2008 (Age 12 to 17 years)	PGA 0 or 1 PASI 75 PASI 90	14/105 12/105 7/105	13 11 7
CAIN457A2310 (estimation Includes simulation uncertainty error)	IGA 0 or 1 PASI 75 PASI 90	7/40 7/40 6/40	17.5 17.5 15

The Meta-Analytic-Predictive (MAP) approach derives an informative prior from historical data which is discounted using a hierarchical model. When using the MAP approach to estimate the predicted placebo response rate, differential discounting was defined for two stratum: pediatric study data and adult study data. Moderate between-trial heterogeneity (with τ prior set as HalfNormal(0, 0.5)) was defined for pediatric trial data and substantial heterogeneity (with τ prior set as HalfNormal(0, 1)) was defined for adult trial data ([Neuenschwander et al. 2010](#)), thus allowing pediatric trial data to be given a higher weight compared to adult trial data. The prior distribution for the regression coefficient β was set as non-informative Normal (0, 2). The following Table 3-2 presents the summary statistics of the fitted mixtures of conjugate distribution to the sample.

All the calculations were performed in the R package RBesT (version 1.3.1) through the meta-analytical-predictive framework ([Spiegelhalter et al. 2004](#), [Neuenschwander et al. 2010](#)).

Table 3-2 Predictive placebo response rates for this study from model of historical data

Endpoint	Mean	Standard Deviation	Median	95% Credible Interval
IGA 0 or 1	9%	6%	8%	1-23%
PASI 75	10%	6%	9%	2-25%
PASI 90	6%	4%	5%	1-18%

Based on confirmatory efficacy in the adult phase III program (CAIN457A2302, CAIN457A2303, CAIN457A2308 and CAIN457A2309), the PASI 75, IGA 0/1 and PASI 90 response rate at week 12 was assumed as 65%, 45% and 39% for secukinumab. Non-informative prior was set for secukinumab arm. A sample size of 40 pediatric patients from this

study under each high or low secukinumab arm over predictive placebo response (Table 3-2) will lead to a power of approximately 99% for each co-primary endpoint and secondary endpoint. Details as following:

- A sample size of 40 pediatric patients per treatment group and true response rates of 65% for PASI 75 and 45% for IGA mod 2011 0 or 1 response for secukinumab was assumed. For each co-primary endpoint there is approximately 99% power to detect a posterior probability of the log odds ratio difference between placebo and secukinumab to exceed with at least 97.5%.
- Similarly, for the secondary endpoint of PASI 90 response there is approximately 99% power to provide a posterior probability of at least 97.5% that the PASI 90 response rate on secukinumab is greater than placebo. This assumes a response rate of 39% for secukinumab.

4 Change to protocol specified analyses

The following are changes to protocol specified analysis:

Following HA recommendation to impute subjects with all post-baseline missing values as non-responders according to the intention to treat principal and to remain consistent with the adult studies and pediatric data used within the MAP analysis, the primary analysis will be performed on pure non-responder imputation and the MI dropped. Modified non-responder analysis may still be performed upon request from HA. No sensitivity analysis will be provided for the Bayesian analysis. For the descriptive summary of key efficacy endpoints, results using pure non-responder imputation as well as multiple imputation will be provided.

Week 16 PEA analysis constitutes the scope for delivering to DMC and an extended FIR requirement, thus a full analysis will not be performed as planned. Further to recent communications with the health authorities, additional outputs and an interim analysis at Week 24 is added to support the pediatric submission. The following subgroup summaries are added to the planned analyses:

- Summaries by age subgroup:<12 years or \geq 12 years
- Summaries by body weight strata:<25kg, 25-<50kg and \geq 50kg
- Summaries by disease severity strata:moderate, severe
- Summaries by body weight and dose group:AIN457 – 75 mg and < 25 kg, AIN457 Low – 75 mg and \geq 25 kg < 50 kg, AIN457 Low – 150 mg and \geq 50 kg; AIN457 High – 150 mg and \geq 25 kg < 50 kg, AIN457 High – 300 mg and \geq 50 kg;

Safety summaries for exposure adjusted incidence rates may be prepared.

Pandemic reporting (COVID-19)

Data collected in this trial that is affected by the COVID-19 situation, can be expected to lead to difficulties in interpretation in the trial's reporting. In recognition of these challenges, both FDA and EMA (and local regulatory authorities) have issued specific guidelines that request

Novartis to collect the reasons for non-compliance and discontinuation of clinical trial elements related to COVID-19 in all ongoing trials.

In adherence to these guidances, specific protocol deviations were added to capture data necessary to provide a summary of impact for the pandemic.

The primary and key secondary objective of the study assessed at Week 12 are not impacted. These were reported prior to the pandemic, which emerged as the last few patients were reaching week 52 visit. Therefore, notably missing data are not expected and imputations are considered reasonable for evaluating efficacy up to week 52.

All protocol deviations for the study will be summarised together (i.e including COVID-19 specific PDs) as described in section 2.3.1. In addition, all protocol deviations from 1st March 2020, that is considered to be the starting point of COVID-19 period (as per internal guidance for those countries participating in this study) will capture whether there was any relation to COVID-19 including a precise relationship status in regard to COVID-19 virus (such as health status related, site issues, quarantine of patient/lockdown, drug supply issue, patient concern, other or no relationship to COVID-19). The relationship status will be presented in the listing. For patients with suspected/confirmed cases of COVID-19, separate summaries and/or listings may be provided for disposition, concomitant medications/procedures and significant non drug therapies and adverse events (including COVID-19 testing with outcome results). Summaries of treatment emergent COVID-19 related adverse events may be presented if data permits.

5 Appendix

Summary statistics for continuous variables will include N, mean, standard deviation, minimum, lower quartile, median, upper quartile, maximum. Summary statistics for discrete variables will be presented in contingency tables and will include absolute and relative frequencies.

5.1 Imputation rules

5.1.1 Study drug

Any partial dates will be imputed as follows:

We take the earlier day of

- The last day in the month and
- The end day of the corresponding epoch

5.1.2 AE date imputation

Impute AE end date:

1. If the AE end date ‘month’ is missing, the imputed end date should be set to the earliest of the (min (last visit date, last dose date + 140 days), 31DECYYYY, date of death).

2. If the AE end date 'day' is missing, the imputed end date should be set to the earliest of the (min (last visit date, last dose date + 140 days), last day of the month, date of death).
3. If AE 'year' is missing or AE is ongoing, the end date will not be imputed.

Impute AE start date:

Before imputing AE start date, find the AE start reference date.

1. If the (imputed) AE end date is complete and the (imputed) AE end date < treatment start date then AE start reference date = min(informed consent date, earliest visit date).
2. Else AE start reference date = treatment start date
 1. If the AE start date 'year' value is missing, the date uncertainty is too high to impute a rational date. Therefore, if the AE year value is missing, the imputed AE start date is set to NULL.
 2. If the AE start date 'year' value is less than the treatment start date year value, the AE started before treatment. Therefore:
 - a. If AE 'month' is missing, the imputed AE start date is set to the mid-year point (01JulYYYY).
 - b. Else if AE 'month' is not missing, the imputed AE start date is set to the mid-month point (15MONYYYY).
 3. If the AE start date year value is greater than the treatment start date year value, the AE started after treatment. Therefore:
 - a. If the AE month is missing, the imputed AE start date is set to the year start point (01JanYYYY).
 - b. Else if the AE month is not missing, the imputed AE start date is set to the later of (month start point (01MONYYYY), AE start reference date + 1 day).
 4. If the AE start date year value is equal to the treatment start date year value:
 - a. And the AE month is missing the imputed AE start date is set to the AE reference start date + 1 day.
 - b. Else if the AE month is less than the treatment start month, the imputed AE start date is set to the mid-month point (15MONYYYY).

c. Else if the AE month is equal to the treatment start date month or greater than the treatment start date month, the imputed AE start date is set to the later of (month start point (01MONYYYY), AE start reference date + 1 day).

If complete (imputed) AE end date is available and the imputed AE start date is greater than the (imputed) AE end date, then imputed AE start date should be set to the (imputed) AE end date.

5.1.3 Concomitant medication date imputation

Impute CM end date:

1. If CM end day is missing and CM month/year are non-missing then impute CM day as the minimum of treatment end date and the last day of the month.
2. If CM end day/month are missing and CM year is non-missing then impute CM day as the minimum of treatment end date and the end of the year (31DECYYYY).
3. If imputed CM end date is less than the CM start date, use the CM start date as the imputed CM end date.

Impute CM start date:

1. If the CM start date year value is missing, the imputed CM start date is set to one day prior to treatment start date.
2. If the CM start date year value is less than the treatment start date year value, the CM started before treatment. Therefore:
 - a. If the CM month is missing, the imputed CM start date is set to the mid-year point (01JulYYYY).
 - b. Else if the CM month is not missing, the imputed CM start date is set to the mid-month point (15MONYYYY).
3. If the CM start date year value is greater than the treatment start date year value, the CM started after treatment. Therefore:
 - a. If the CM month is missing, the imputed CM start date is set to the year start point (01JanYYYY).
 - b. Else if the CM month is not missing, the imputed CM start date is set to the month start point (01MONYYYY).
4. If the CM start date year value is equal to the treatment start date year value:

- a. And the CM month is missing or the CM month is equal to the treatment start date month, then the imputed CM start date is set to one day prior treatment start date.
- b. Else if the CM month is less than the treatment start date month, the imputed CM start date is set to the mid-month point (15MONYYYY).
- c. Else if the CM month is greater than the treatment start date month, the imputed CM start date is set to the month start point (01MONYYYY).

If complete (imputed) CM end date is available and the imputed CM start date is greater than the (imputed) CM end date, then imputed CM start date should be set to the (imputed) CM end date.

5.1.3.1 Prior therapies date imputation

See Section 5.1.3.

5.1.3.2 Post therapies date imputation

See Section 5.1.3.

5.1.3.3 First diagnosis date (Pso, PsA) imputation

1. If the first diagnosis day/ month are missing and the year is non-missing:
 - a. If the year part of the first diagnosis date is equal to the year part of the inform consent date, then the imputed first diagnosis date is set to the year start point (01JanYYYY).
 - b. Otherwise the imputed first diagnosis date is set to the mid-year point (01JulYYYY).
2. If the first diagnosis day is missing and the month/year are non-missing:
 - a. If the month and year part of the first diagnosis date is equal to the month and year part of the inform consent date, then the imputed first diagnosis date is set to the month start point (01MONYYYY).
 - b. Otherwise the imputed first diagnosis date is set to the mid-month point (15MONYYYY).

5.1.3.4 Other imputations

Only PASI and IGA mod 2011 based response variables are imputed with multiple imputation or non-response, other response variables (██████████) will be imputed with LOCF.

For laboratory test values below Lower Level of Quantification (LLQ) or above Upper Level of Quantification (ULQ) will be imputed as LLQ or ULQ value, respectively. The numerical part of the reported result will be treated as the actual LLQ or ULQ. These laboratory values will be displayed in listings using the standard unit with the reported sign (“<” or “>”).

5.2 AEs coding/grading

Adverse events will also be coded according to MedDRA dictionary, using a narrow search. The MedDRA version used for reporting the adverse events will be described in a footnote.

Safety topics of interest, such as risks defined in the Safety Profiling Plan, Risk Management Plan or topics of interest regarding signal detection or routine analysis are defined in the Program Case Retrieval Sheet.

5.3 Laboratory parameters derivations

Not applicable.

5.4 Statistical models

5.4.1 Analysis of continuous data

Summary statistics (including N, mean, standard deviation, minimum, lower quartile, median, upper quartile, maximum) will be provided for continuous data by visit and treatment group. If applicable, means +/- SE will be plotted.

5.4.2 Analysis of binary (and categorical) data

Summary statistics for discrete variables will be presented in contingency tables and will include absolute and relative frequencies. If applicable, confidence intervals will be derived as well based on the score method including continuity correction [Newcombe (1998)].

With Z as (1-alpha/2)-quantile of the standard normal distribution (SAS: $z=PROBIT(1-\alpha/2)$), n as total number of subjects (i.e. number of subjects in the denominator), and p as estimated crude incidence (number of subjects with event / n) it is $q=1-p$

Then the lower limit is for $p > 0$, ($L = 0$ for $p = 0$),

$$L = \max\left(0, \frac{2np + z^2 - 1 - z\sqrt{z^2 + 2 - \frac{1}{n} + 4p(nq+1)}}{2(n+z^2)}\right)$$

and the upper limit is for $p < 1$, ($U = 1$ for $p = 1$),

$$U = \min\left(1, \frac{2np + z^2 + 1 + z\sqrt{z^2 + 2 - \frac{1}{n} + 4p(nq-1)}}{2(n+z^2)}\right)$$

Figures will be provided for PASI 75 response (upper left) PASI 90 response (upper right), PASI 100 response (lower left) and IGA mod 2011 0 or 1 response (lower right) at Week 12 and Week 16 as dot plots displaying treatments on the x-axis and point estimates including 95% confidence intervals on the y-axis.

For time courses of response variables, the point estimate at each time point including 95% confidence interval will be plotted.

5.4.3 Multiple imputations for response variables

Descriptive summaries for PASI 75, PASI 90, PASI 100 and IGA mod 2011 0 or 1 response by visits will be analyzed using multiple imputation method.

In the multiple imputations analysis the response status will be imputed based on the individual treatment arm information.

Multiple imputation (MI) is a simulation based approach where missing values are replaced by multiple Bayesian draws from the conditional distribution of missing data given the observed data and covariates, creating multiple completed data sets. These completed data sets can then be analyzed using standard methods. [Rubin \(1987\)](#) presented rules how to combine the multiple sets of estimates to produce overall estimates and confidence intervals that adequately incorporate missing data uncertainty.

Missing values for the 'change from baseline PASI score' and 'IGA mod 2011 score' will be imputed simultaneously based on an underlying joint normal distribution and using a Markov Chain Monte Carlo (MCMC) method. The change from baseline in PASI score appears to follow closer to a normal distribution than the actual PASI score. Assuming normality for the 'IGA mod 2011 score' is motivated by [Schaefer \(1997\)](#), where it was shown that the multivariate normal approximation for the imputation of incomplete categorical and binary data is robust.

The imputations will be done separately for each treatment group including baseline weight, failure to at least one previous biologic (yes/no), and number of previous systemic therapies as additional covariates.

Summary statistics for PASI 75, PASI 90, PASI 100, and IGA mod 2011 0 or 1 response by visit will be presented in contingency tables with multiple imputations method.

The number of imputations will be set to 100, the seed for the random function will be set to 4572311 for this study. SAS procedure MI will be used to generate the multiple imputed data sets. The SAS procedure MI can be used as follows:

The input data set <pasi_iga> should have one record per subject with baseline PASI score and IGA mod 2011 score as well as all changes from baseline PASI and post-baseline IGA mod 2011 score.

```
ODS LISTING CLOSE;
ODS OUTPUT MissPattern=msgpat VarianceInfo=varinfo ParameterEstimates=param;
PROC MI DATA=<pasi_iga> OUT=<impdata> SEED=457<studycode> NIMPUTE=100;
VAR <baseline weight> <failure to at least one biologic>
<number of previous systemic therapies>
```

```
<baseline PASI> <baseline IGA>
<change from baseline PASI week 1> - <change from baseline PASI week primary endpoint>
<IGA week1> - <IGA week primary endpoint>;
EM converge=1E-2 MAXITER=5000;
MCMC PRIOR=RIDGE=2 ;
BY <treatment group>;
RUN;
ODS LISTING;
```

Programming notes:

The SAS procedure MIANALYZE expects a variable called “_IMPUTATION_” which is generated by the MI procedure. It might be needed to set the SAS option “VALIDVARNAME=UPCASE” temporarily in the program before the MI call, this option should be reset after the MIANALYZE call to VALIDVARNAME=V6. In case there are no missings in one treatment group, the MI procedure does not impute any values. In this case the corresponding data need to be imputed manually outside PROC MI and added to the dataset <impdata>.

The imputed data are saved in data set <impdata>. The outcomes of interest, i.e. the PASI 50/75/90/100 response and IGA mod 2011 0 or 1 response will be calculated, e.g. as follows:

```
DATA <impdata2>;
SET <impdata>;
IF <change from baseline PASI week primary endpoint>/<baseline PASI>=0.75 THEN <PASI 75 response> =1;
ELSE <PASI 75 response>=0;
<...repeat for all PASI response...>
IF <baseline IGA>=3 THEN DO;
IF <IGA week primary endpoint> < 1.5 THEN <IGA 0/1 response> =1;
ELSE IF <IGA week primary endpoint> >=1.5 THEN <IGA 0/1 response> =0;
ELSE PUT "E" "RROR:" stysid1a=;
END;
ELSE IF <baseline IGA>=2 THEN DO;
IF <IGA week primary endpoint> < 0.5 THEN <IGA 0/1 response> =1;
ELSE IF <IGA week primary endpoint> >=0.5 THEN <IGA 0/1 response> =0;
ELSE PUT "E" "RROR:" stysid1a=;
END;
ELSE <IGA 0/1 response> =0;
RUN;
```

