#### **9.4.3 Handling of missing values/censoring/discontinuations**

The following imputation methods will apply to the missing data for analysis up to Week 52.

- Pure non-responder imputation (includes Bayesian Primary endpoint analysis at Week 12): Missing values with respect to response variables based on PASI score and IGA mod 2011 categories were to be imputed with non-response regardless to the reason for missing data (e.g. premature study discontinuation, missed visit, administrative issues). Patients with missing baseline or those with all post-baseline missing were to be imputed with non-response (in the secukinumab treatment groups).
- Descriptive summaries on response variables based on PASI score and IGA mod 2011 categories will be imputed with multiple imputations (MI) method as sensitivity imputation method. Multiple imputation (MI) is a simulation based approach where

missing values are replaced by multiple Bayesian draws from the conditional distribution of missing data given the observed data and covariates, creating multiple completed data sets. These completed data sets can then be analyzed using standard methods. Within this analysis the PASI score (absolute change from baseline) or IGA mod 2011 categories will be imputed and response variables will be derived based on the imputed scores. In the multiple imputation analysis the response status will be imputed based on the individual treatment arm information.

The following imputation methods will apply to the missing data for analysis of the long term data beyond Week 52:

- Response variables based on PASI score and IGA mod 2011 categories will be generally be presented as 'observed case'; i.e. all available data for each time point will be included in the analyses.
- Summaries on multiple imputation will be provided as sensitivity analysis where appropriate.

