The investigator is responsible for collecting the components or scoring signs and total regional area for all visits. PASI and total BSA calculations will be performed by investigator at screening and randomization only. The PASI scores will be calculated by Novartis and will be used in the analysis and for derivation of PASI response values (see below). [REDACTED]

[REDACTED]

Table 2-6 The PASI scoring system

Body region	Erythema (E)	Thickening (plaque elevation, induration, I)	Scaling (desquamation, D)	Area score (based on true area %, A)*
Head (H) [†]	0=none	0=none	0=none	0 = no involvement
	1=slight	1=slight	1=slight	1 = >0-<10%
	2=moderate	2=moderate	2=moderate	2 = 10-<30%
	3=severe	3=severe	3=severe	3 = 30-<50%
	4=very severe	4=very severe	4=very severe	4 = 50-<70%
				5 = 70-<90%
Trunk (T) [‡]	0=none	0=none	0=none	6 = 90-100%
	1=slight	1=slight	1=slight	0 = no involvement
	2=moderate	2=moderate	2=moderate	1 = >0-<10%
	3=severe	3=severe	3=severe	2 = 10-<30%
	4=very severe	4=very severe	4=very severe	3 = 30-<50%
				4 = 50-<70%
Upper limbs (U)	0=none	0=none	0=none	5 = 70-<90%
	1=slight	1=slight	1=slight	6 = 90-100%
	2=moderate	2=moderate	2=moderate	0 = no involvement
	3=severe	3=severe	3=severe	1 = >0-<10%
	4=very severe	4=very severe	4=very severe	2 = 10-<30%
				3 = 30-<50%
Lower limbs (L) [§]	0=none	0=none	0=none	4 = 50-<70%
	1=slight	1=slight	1=slight	5 = 70-<90%
	2=moderate	2=moderate	2=moderate	6 = 90-100%
	3=severe	3=severe	3=severe	0 = no involvement
	4=very severe	4=very severe	4=very severe	1 = >0-<10%
				2 = 10-<30%

* Percentage (not score) of body region (not whole body) affected will be entered in the eCRF.

[†] Neck is assessed as part of the Head (H) body region.

[‡] Axillae and groin are assessed as part of the Trunk (T) body region.

[§] Buttocks are assessed as part of the Lower limbs (L) body region.

The following definitions are possible efficacy evaluations that can be used in clinical trials in psoriasis ([CHMP/EWP/2454/02, 2004](#)):

- **PASI 75 response:** subjects achieving $\geq 75\%$ improvement (reduction) in PASI score compared to baseline are defined as PASI 75 responders
- **PASI 90 response:** subjects achieving $\geq 90\%$ improvement (reduction) in PASI score compared to baseline are defined as PASI 90 responders

2.5.1.2 Definition of IGA mod 2011 score and IGA mod 2011 0 or 1 response

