2.8.3 Laboratory data

The summary of laboratory evaluations will be presented for two groups of laboratory tests (hematology and serum chemistry).

The general guideline for laboratory summaries (including vital signs and ECGs in Section 2.8.4.1 and 2.8.4.2) are as below:

- all the summary of laboratory outputs (newly occurring notables, maximum changes, shift tables, by visit summary statistics) will be reported on all data collected up until end of study. Any summary presented by period will use the on-treatment definition i.e., include all assessments within last dose plus 84 days.
- all records are displayed in the listing with the on-treatment flag. i.e., occurred within last dose plus 84 days- yes or no, as well as eCRF visits and period.

Descriptive summary statistics for the change from baseline to each study visit will be presented by laboratory test and treatment group. Change from baseline will only be summarized for subjects with both baseline and post baseline values and will be calculated as:

$$\text{change from baseline} = \text{post baseline value} - \text{baseline value}$$

For laboratory test values below Lower Level of Quantification (LLQ) or above Upper Level of Quantification (ULQ) will be imputed as LLQ or ULQ value, respectively. The numerical part of the reported result will be treated as the actual LLQ or ULQ. These laboratory values will be displayed in listings using the standard unit with the reported sign (“<” or “>”).

For each parameter, the maximum change (maximum decrease and maximum increase) from baseline within treatment period will be summarized analogously.

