2.8.4.2 Vital signs

Analysis in vital sign measurement using descriptive summary statistics for the change from baseline for each post-baseline visit will be performed by vital sign and treatment group. Change from baseline will only be summarized for subjects with both baseline and post - baseline values and will be calculated as:

$$\text{change from baseline} = \text{post-baseline value} - \text{baseline value}$$

Vital signs will be summarized by visit based on the entire study period data. All vital signs will be listed with “on-treatment” flag displayed.

[figure not shown]
The number and percentage of subjects with newly occurring notable vital signs (within the treatment period) will be presented by treatment group. Subjects not meeting the following criteria at baseline but meeting at post-baseline are considered to be subjects with newly occurring abnormalities. Criteria for notable vital sign abnormalities are provided in Table 2-13 below:

[figure not shown]
Table 2-13 Criteria for notable vital signs in pediatric patients

Age group	Systolic BP(mmHg)	Diastolic BP(mmHg)	Pulse (bpm)
6 -11 yrs	90-130	50-80	50-105
12-17 yrs	90-145	55-90	45-95
18 yrs and over	90-139	60-89	60-100

If appropriate, data of subjects with newly occurring notable vital signs abnormalities will be listed in an additional listing.

Of note, systolic and diastolic blood pressure will be measured twice (measurements separated by 1 to 2 minutes), the average will be entered on the Vital Signs eCRF and will be used in the analysis.

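### Does the SAP's example code for PASI response after multiple imputation count worsening as response?

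*SAP*

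**What the plan says.** SAP 5.4.3 imputes PASI change from baseline jointly with the IGA score and then derives response. The derivation is introduced as an illustration: "IGA mod 2011 0 or 1 response will be calculated, e.g. as follows". The PASI 75 line reads "<change from baseline PASI week primary endpoint>/<baseline PASI>=0.75 THEN" response is set to 1, with a note to repeat it for all PASI responses. The July 2020 and September 2023 SAPs print the same line.

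The variable is named without a direction. SAP 5.4.3 says "The change from baseline in PASI score appears to follow closer to a normal distribution than the actual PASI score", and Protocol 9.4.3 says "Within this analysis the PASI score (absolute change from baseline) or IGA mod 2011 categories will be imputed"; neither gives a formula.

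The direction of response itself is stated. SAP 2.5.1.1 requires at least a 75% "improvement (reduction) in PASI score compared to baseline are defined as PASI 75 responders". PASI 90 is worded the same way, and Protocol 6.4.2 and 9.4.1 agree.

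The change-from-baseline formulas that can be read in the SAP are in 2.8.3 (laboratory data) and 2.8.4.2 (vital signs). Both are post-baseline minus baseline, and neither mentions PASI.

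**The concern.** Someone who carries the safety formula over to PASI gets the opposite of the response definition. The IGA lines in the same data step count a low score as success, so a patient going from PASI 20 and IGA 3 to PASI 2 and IGA 0 would be an IGA responder but a PASI 75 and PASI 90 non-responder.

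The error would not be confined to imputed values. The step reads the whole completed data set, and for an arm without missing values the programming note says "In this case the corresponding data need to be imputed manually outside PROC MI and added to the dataset <impdata>", so observed data pass through the same rule.

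At stake are the multiple-imputation summaries of PASI response. They are the supportive analysis beside non-responder imputation up to Week 52 (SAP 2.5.4 and Section 4) and an optional sensitivity method afterwards. No sensitivity analysis is planned for the Bayesian comparison, so these summaries are the named check on missing-data handling for PASI.

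**Working it through.** **Inputs.** Cut-offs 0.50, 0.75, 0.90 and 1.00 (SAP 5.4.3); response as a proportional reduction (SAP 2.5.1.1); PASI range 0 to 72 (SAP 2.5.1.1); baseline PASI at least 12 (Protocol 4.1); 40 patients per arm and 65% PASI 75 response (SAP Section 3). The operator is read as at-least. As printed, the closing bracket of the placeholder runs into an equals sign, but an equality test makes no sense for a continuous ratio.

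**Single patients, cut-off 0.75.**

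| Baseline → Week 12 | (post − base)/base | (base − post)/base | Responder by 2.5.1.1 |
|---|---|---|---|
| 20 → 5 | −0.75 | +0.75 | yes |
| 20 → 0 | −1.00 | +1.00 | yes |
| 20 → 35 | +0.75 | −0.75 | no |

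The positive threshold gives the right answer in the third column and the wrong one in the second.

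**Whole scale.** Take baseline 12 to 72 and post-baseline 0 to 72 in steps of 0.4: 151 × 181 = 27,331 pairs, compared in exact arithmetic.

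- Change held as baseline minus post: the code agrees with the definition in 27,331 of 27,331 pairs at each of the four cut-offs.
- Change held as post minus baseline, cut-off 0.75: 4,754 pairs are flagged. All are worsening, and none is among the 4,058 true-responder pairs. The other three cut-offs also flag only worsening.
- A false PASI 75 response needs post-baseline PASI of at least 1.75 × baseline. With a ceiling of 72, it is impossible above a baseline of 72/1.75 = 41.1.

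So one storage convention reproduces the definition exactly and the other fails it completely.

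**Would a reversed sign go unnoticed?** At the planned rate, 0.65 × 40 = 26 patients per arm respond. Suppose 5% or 10% are missing at Week 12, unrelated to outcome (assumed; the documents give no rate). Non-responder imputation then gives 0.65 × 0.95 = 61.8% or 0.65 × 0.90 = 58.5%, and multiple imputation coded correctly gives about 65%. Coded backwards, it counts only patients whose PASI rose by at least 75%. Simulation with baseline PASI around 20 (SD 6, at least 12) and improvement calibrated to the planning rates gives 0.0% with normal tails and 3.4% with the most extreme tails tried (t with 1 df). SAP Section 4 has both sets of results provided for the key efficacy endpoints, so the comparison would be of roughly 0% with roughly 60%.

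**Reach.** The Bayesian co-primary and key secondary analyses use pure non-responder imputation (SAP 2.5.3 and 2.6.3). IGA response under multiple imputation has its own lines. The power calculation uses none of this code.

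**The case for a change.** The strongest opposing case is that this is the only rule shown for turning imputed PASI values into response, in a section careful enough to fix the seed and the number of imputations. It survived unchanged from 2020 to 2023, a plan should not depend on implausible output to reveal a sign, and one sentence would settle it.

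The factual part stands: in the text available, 5.4.3 states no direction and prints an unclear operator, and under post minus baseline the rule is exactly wrong.

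Three things limit it. First, it cannot be shown that the safety formula is the SAP's only convention. Section 2.7, where the change logs place the other efficacy analyses and the missing-data methods after Week 52, is not visible in either version, and text in 2.5.1.1 next to the derivation of PASI response is redacted. Such gaps cannot be held against the plan. Second, nothing extends the laboratory and vital-sign formulas to PASI, whereas the efficacy sections speak throughout of reduction, which fits a positive threshold. Third, the code cannot be run as printed: the programmer must supply variable names, settle the operator and fill in the other cut-offs, and in doing so works from the written definition of response.

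**Conclusion.** No change to the plan is needed. The missing sign is a detail that an analyst fills from the response definition in SAP 2.5.1.1, and only one choice is compatible with that definition. The documents do not show that worsening is, or was, counted as response, nor which sign the production program used.

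If the sign were reversed, the PASI 75 rate under multiple imputation would drop by about 61–65 percentage points, against an expected gap of about 3–6 points between multiple and non-responder imputation. These sizes rest on the planned response rates and on assumed baseline scores, tails and missing rates. An error that large would show when the two methods are set side by side, or when observed Week 12 responses are compared between them in routine program checking. The exposure is confined to supportive, descriptive PASI summaries; no primary or key secondary result or conclusion depends on the line.
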